9.3 Informed Consent

The investigator or qualified designee must obtain documented consent according to ICH-GCP and local regulations, as applicable, from each potential subject or each subject's legally authorized representative prior to participating in the research study. Subjects who agree to participate will sign the approved informed consent form and will be provided a copy of the signed document.

The initial ICF, any subsequent revised written ICF and any written information provided to the subject must be approved by IRB prior to use. The ICF will adhere to IRB requirements, applicable laws and regulations.

9.4 Compliance with Trial Registration and Results Posting Requirements

Under the terms of the Food and Drug Administration Modernization Act (FDAMA) and the Food and Drug Administration Amendments Act (FDAAA), the Sponsor-Investigator of the trial is solely responsible for determining whether the trial and its results are subject to the requirements for submission to <http://www.clinicaltrials.gov>. Information posted will allow subjects to identify potentially appropriate trials for their disease conditions and pursue participation by calling a central contact number for further information on appropriate trial locations and trial site contact information.

9.5 Record Retention

Essential documents are those documents that individually and collectively permit evaluation of the study and quality of the data produced. After completion of the study, all documents and data relating to the study will be kept in an orderly manner by the Investigator in a secure study file. Essential documents should be retained for 2 years after the final marketing approval in an ICH region or for at least 2 years since the discontinuation of clinical development of the IP. In addition, all subjects medical records and other source documentation will be kept for the maximum time permitted by the hospital, institution, or medical practice.

10. Statistical Considerations

10.1 Study Design/Endpoints

We hypothesize that in the transition from a standard antiretroviral regimen to a BIC/F/TAF regimen, there would be high probability of a sustained suppression of HIV- RNA (1). In the randomized, double-blind, multicenter, active-controlled, phase 3, non-inferiority clinical trial of switching to fixed-dose bicitegravir, emtricitabine, and tenofovir alafenamide from dolutegravir plus abacavir and lamivudine in virologically suppressed adults with HIV-1 by Molina et al, the primary endpoint was the proportion of participants with plasma HIV-1 RNA of 50 copies per mL or higher at week 48 fulfilled the prespecified non-inferiority margin of 4%, where three (1%) of 282 in the bicitegravir group had HIV-1 RNA of 50 copies per mL or higher at week 48 versus one (<1%) of 281 participants in the dolutegravir group (difference 0.7%, 95.002% CI-1.0 to 2.8; p=0.62).

The number of 20 subjects who are projected for enrollment will provide sufficiently robust data for pharmacokinetic studies to yield a coefficient of variation of <15%, which will permit a robust analysis and model development. Outcome variables and adverse events will be reported using descriptive statistics, including means, medians, ranges, and standard errors. The relationship between renal function, tacrolimus levels, BIC/F/TAF plasma concentrations, and intracellular concentrations of TAF will be determined by linear regression analysis.

Expected Outcomes:

1. We expect sustained suppression of the HIV viral load throughout the study.
2. We expect that BIC/F/TAF will be well tolerated in the HIV+ renal transplant population with minimal adverse events and preservation of renal function with stable tacrolimus levels.
3. Plasma concentrations of BIC/F/TAF will follow those reported in HIV+ non-renal transplant recipients and drug/drug interactions with tacrolimus will be minimal, allowing easy adjustment with minimal detrimental effects on renal function.

11. Adverse Events

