Short Title:	Switch to BIC/FTC/TAF after Renal Transplant
Clinical Phase:	IV
Principal Investigator:	[name]
Study Description:	Hypothesis: We hypothesize that BIC/F/TAF will be efficacious and safe in the management of HIV+ post renal transplant patients, and will have few adverse reactions and drug-drug interactions with tacrolimus in this population
Sample Size:	N = 20
Study Population:	Virally-suppressed HIV+ adults post-renal transplant
Enrollment Period:	November 2020 to May 2023
Study Design:	Single arm, open-label, switch study, following subjects for 48 weeks with a 6 month follow-up
Study Duration:	November 2020 – December 2024
Participant Duration:	In this single arm, open-label, switch study, we propose to switch virally suppressed HIV+ adults post-renal transplant to BIC/F/TAF and follow the subjects for 48 weeks with a 6 month follow-up (Section 6.1).
Study Agent:	BIC/F/TAF® (BIC/F/TAF)
Primary Objectives:	
 1. To determine the efficacy of BIC/F/TAF in HIV+ patients post renal transplant at 24 weeks and 48 weeks post-switch to BIC/F/TAF. 2. To assess the safety and tolerability of BIC/F/TAF in HIV+ patients post renal transplant at 24 weeks and 48 weeks post-switch to BIC/F/TAF. 3. To assess the pharmacokinetics of BIC/F/TAF in HIV+ patients post renal transplant and its interactions with immunosuppressive agents (Tacrolimus) at 12 weeks post-switch to BIC/F/TAF. 4. To assess renal biomarkers including urine protein/creatinine ratio; urine albumin/creatinine ratio; eGFR; serum BUN, creatinine and phosphorus; tacrolimus levels; retinol 2 binding protein and B2 microglobulin post renal transplant at 24 weeks and 48 weeks post-switch to BIC/F/TAF.
Secondary Objectives:	
 1. To assess the incidence of kidney graft rejection after switching to BIC/F/TAF post renal transplant at 24 weeks and 48 weeks post-switch to BIC/F/TAF. 2. To assess the immunologic activity (CD4 count/percentage) of BIC/F/TAF post renal transplant in conjunction with immunosuppressive agents (tacrolimus) at 24 weeks and 48 weeks post-switch to BIC/F/TAF. 3. To determine patient satisfaction with BIC/F/TAF post renal transplant by utilizing a questionnaire to assess health-related quality of life outcomes at 24 weeks and 48 weeks post-switch to BIC/F/TAF.

Primary Endpoints:

1. Proportion of subjects with plasma HIV-1 RNA <50 copies/ml at week 48.

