3.1 Overall Design

We hypothesize that BIC/F/TAF will be efficacious and safe in the management of HIV+ post renal transplant patients, and will have few adverse reactions and drug-drug interactions with tacrolimus in this population.

Eighteen subjects will be enrolled in this Phase IV, single arm, open-label, single-site, switch study. In this study, virally suppressed HIV+ adults will be switched post-renal transplant from their current anti-retroviral regimen to BIC/F/TAF and will be followed for 48 weeks with a 6 month follow-up (Section 6.1). Informed consent will be obtained before starting the study (Section 6.1).

Patients will have bloodwork completed throughout the study, as shown in the Schedule of Assessments (Section 6.1).

A health-related quality of life questionnaire (Appendix) will be administered to each patient to assess satisfaction with a one pill regimen as well as adverse events (Section 6.1).

Pharmacokinetic (PK) studies will be assessed at Week 12 when the renal function is stable (decided by PI). Intracellular TAF levels by dried blood spot will be collected during the Week 12 visit as well as Week 24, Week 36, Week 48, Month 6 Follow-up. Intracellular TAF levels by PBMC will be collected once during the Week 12 visit. An intensive pharmacokinetic day will take place at the Week 12 visit. This bloodwork is outlined in Section 6.1. Bloodwork for the intracellular TAF level testing and pharmacokinetic testing will be stored and sent to [name] at the University of Colorado's Antiviral Laboratory. (14-16)

Note: Patients switched post-renal transplant from their current anti-retroviral regimen to BIC/F/TAF prior to identification for this study may also be enrolled. This group will be referred to as "Group 2". Pharmacokinetic testing for Group 2 subjects will be completed once each Group 2 subject's tacrolimus levels are stable as per the Principal Investigator for 2-4 weeks. All standard of care lab values and concomitant medications will be collected from Group 2 subjects for 60 days prior to and after the Biktarvy switch date and for the duration of Biktarvy therapy. Any adverse events related to Biktarvy prior to enrollment will be recorded.

Sample Collection

Samples include plasma and peripheral blood mononuclear cells (PBMC). Blood is collected in EDTA tubes for plasma separation. CPT vacutainers are used to isolate PBMC, which are counted with an

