automated countess cytometer (Invitrogen™, Thermo Fisher Scientific Corporation, Carlsbad, CA) and lysed. BIC, F, and TAF in plasma are assayed using a validated LC/MS/MS methodology with a lower limit of quantification (LLOQ) of 10 ng/mL (16).

Determination of Pharmacokinetic Variables

The pharmacokinetic variables for BIC/F/TAF are calculated from the concentration-time data using noncompartmental methods. The peak drug concentration (C_{max}) and time of peak drug concentration are obtained directly from the observed data. The terminal elimination rate constant (k_{el}) is obtained from a log-linear regression of the plasma concentration compared to time data in the terminal post distribution phase. The elimination half-life ($t_{1/2}$) is calculated from $0.693/k_{el}$. The area under the plasma drug concentration-versus-time curve (AUC_{0-24}) and the area under the moment curve from 0 to 24 h ($AUMC_{0-24}$) are calculated by the log-linear trapezoidal rule. The area under the plasma drug concentration-versus-time curve from time zero to time infinity ($AUC_{0-\infty}$) is obtained from the following equation: $AUC_{0-24} \cdot C_t/k_{el}$, where C_t is the last measurable concentration and k_{el} is the terminal elimination rate constant. The total body clearance (CL) is obtained from the equations $dose/AUC_{0-\infty}$ and $dose/AUC_{0-24}$ (presumed steady state, where 24 h is the dosing interval), respectively. The volume of distribution (V_d) is calculated as follows: $V_d = CL/k_{el}$. The steady-state volume of distribution (V_{ss}) is calculated from the product of CL and the mean residence time. The mean residence time is obtained from the following equation: $(AUMC_{0-\infty}/AUC_{0-\infty}) T/2$, where $AUMC_{0-\infty}$ is extrapolated from $[(C_t \times t)/k_{el} \times C_t/k_{el}]$ and where T is the infusion time, all other terms having been previously defined.

Statistical Analyses and Sample Size

This is a pilot study of the efficacy, safety, and pharmacokinetics of BIC/F/TAF in HIV+ renal transplant recipients. Sample size is based upon feasibility of enrolling the current cohort of patients on the WCM/NYPH renal transplant service who are currently receiving antiretroviral therapy. Among the 37 HIV+ renal transplant recipients who are followed at NYPH and who are currently eligible for the study, we project that 20 patients will enroll into this study and complete treatment.

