We hypothesize that in the transition from a standard antiretroviral regimen to a BIC/F/TAF regimen, there would be high probability of a sustained suppression of HIV- RNA (1). In the randomized, double-blind, multicenter, active-controlled, phase 3, non-inferiority clinical trial of switching to fixed-dose bictegravir, emtricitabine, and tenofovir alafenamide from dolutegravir plus abacavir and lamivudine in virologically suppressed adults with HIV-1 by Molina et al, the primary endpoint was the proportion of participants with plasma HIV-1 RNA of 50 copies per mL or higher at week 48 that fulfilled the prespecified non-inferiority margin of 4%, where three (1%) of 282 in the bictegravir group had HIV-1 RNA of 50 copies per mL or higher at week 48 versus one (<1%) of 281 participants in the dolutegravir group (difference 0.7%, 95.002% CI -1.0 to 2.8; $p=0.62$).

The number of 20 subjects who are projected for enrollment and study completion will provide sufficiently robust data for pharmacokinetic studies to yield a coefficient of variation of <15%, which will permit a robust analysis and model development.

Outcome variables and adverse events will be reported using descriptive statistics, including means, medians, ranges, and standard errors.

The relationship between renal function, tacrolimus levels, BIC/F/TAF plasma concentrations, and intracellular concentrations of TAF will be determined by linear regression analysis.

4. Subject Selection

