4.6 Strategies for Recruitment and Retention

The Renal Transplant Program works in close collaboration with the Transplant/Oncology Infectious Diseases Program, including clinical research trials. Recruitment will primarily rely on referrals from the Renal Transplant Program and/or existing patients of the infectious disease investigators. Recruitment will primarily be sources from outpatient clinics, such as the Infectious Disease Clinic and the Renal Transplant Clinic. The target enrollment is 20 subjects. Monthly enrollment logs will be collected.

Subjects will be compensated \$40 per outpatient visit, as a stipend to cover travel costs. For visits that require pharmacokinetic blood sampling, subjects will be compensated \$200 per outpatient visit, as a stipend to cover travel costs and time.

5. Registration Procedures

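### The standard error is the only precision measure named and no confidence interval is planned for the binary week-48 endpoint, so a 20/20 result would carry a standard error of 0

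*Combined protocol and SAP*

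**What the plan says.** The synopsis lists as first primary endpoint "Proportion of subjects with plasma HIV-1 RNA <50 copies/ml at week 48". Adverse events are also a primary endpoint, and the incidence of graft rejection is a secondary one. All of these are counts of subjects with or without an event, or can be reported that way.

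The descriptive analysis is stated twice in the same words, in Section 3.1 (under Statistical Analyses and Sample Size) and in Section 10.1: "Outcome variables and adverse events will be reported using descriptive statistics, including means, medians, ranges, and standard errors". Neither section, nor any other, plans a confidence interval, exact method, test, null rate or success threshold for the week-48 proportion. The only confidence interval in the documents belongs to the cited phase 3 switch trial.

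The sample size rests on feasibility: "Sample size is based upon feasibility of enrolling the current cohort of patients". Section 3.1 adds "we project that 20 patients will enroll into this study and complete treatment", and Section 4.6 says "The target enrollment is 20 subjects". Section 3.1 also states "Eighteen subjects will be enrolled in this Phase IV, single arm, open-label, single-site, switch study". The one precision target attached to 20 subjects is a coefficient of variation for pharmacokinetics, which does not bear on the proportion.

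On the expected result, Section 10.1 says "We expect sustained suppression of the HIV viral load throughout the study", and both statistical sections hypothesise that "there would be high probability of a sustained suppression of HIV- RNA".

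**The concern.** Means, medians and ranges say little about a yes/no outcome. Of the statistics listed, only the standard error could convey how uncertain the week-48 proportion is. The usual standard error of a proportion is estimated from the observed proportion, so it vanishes when every subject, or no subject, has the event. The plan expects results at or close to that boundary: subjects enter already suppressed (Section 4.2 requires at least three months) and are expected to stay so.

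What is at stake is how the result reads. A report of 100% with a standard error of 0 gives no sign that 20 patients cannot exclude an appreciable failure rate. The same holds for a toxicity or a graft rejection that is simply not observed, in a population for which the protocol says long-term renal safety of the tenofovir component alongside tacrolimus is unknown.

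**Working it through.** **Inputs.** n = 20 (synopsis, Sections 3.1, 4.6 and 10.1); n = 18 as a sensitivity case (Section 3.1); binary endpoint (synopsis); the standard error as the only precision measure (Sections 3.1 and 10.1); 3 of 282 subjects with HIV-1 RNA of 50 copies/mL or higher at week 48 in the cited trial (Sections 3.1 and 10.1).

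**1. The plan's own figure.** There is none to reproduce: N = 20 comes from feasibility, and no precision is stated for the proportion. The cited trial's difference does reproduce: 3/282 − 1/281 = 1.06% − 0.36% = 0.71%, stated as 0.7%.

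**2. Standard error.** SE = √(p(1 − p)/n).
- 20/20: √(1 × 0/20) = 0. Using n − 1 as divisor also gives 0.
- 19/20: √(0.95 × 0.05/20) = 0.0487, or 4.9 points (5.0 with n − 1).

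**3. Exact limits at the boundary.** When all n subjects respond, the lower Clopper-Pearson limit of a two-sided 95% interval solves pⁿ = 0.025.
- 20/20: 0.025^(1/20) = 0.832, so 83.2% to 100%.
- 18/18: 0.025^(1/18) = 0.815, so 81.5% to 100%.
- 0/20 for an adverse event: upper limit 1 − 0.832 = 0.168, so 0% to 16.8%.

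**4. Results at and near the boundary.**

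| Suppressed | SE (points) | Exact 95% CI | Wilson 95% CI |
|---|---|---|---|
| 20/20 | 0 | 83.2–100% | 83.9–100% |
| 19/20 | 4.9 | 75.1–99.9% | 76.4–99.1% |
| 18/20 | 6.7 | 68.3–98.8% | 69.9–97.2% |
| 18/18 | 0 | 81.5–100% | 82.4–100% |
| 17/18 | 5.4 | 72.7–99.9% | 74.2–99.0% |

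**5. What a reader might build from the standard error.** At 19/20, 0.95 ± 1.96 × 0.0487 gives 85.4% to 104.6%, against the exact 75.1% to 99.9%. The upper limit is impossible and the lower limit is about 10 points higher than the exact one. The plan does not specify this interval; the figure is illustrative.

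**6. How likely 20/20 is.** The documents give no expected rate for transplant recipients, so the true rate is an assumption. P(20/20) = pⁿ:
- 90%: 0.90²⁰ = 12%
- 95%: 0.95²⁰ = 36%
- 97%: 0.97²⁰ = 54%
- 98.9% (1 − 3/282, borrowed from the cited trial): 81%
- 99%: 0.99²⁰ = 82%

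**The case against.** The strongest reply is that the sentence is generic. It covers pharmacokinetic parameters, tacrolimus levels, renal biomarkers, CD4 counts and questionnaire scores, and medians and ranges suggest it was written with those in mind. It is also introduced by a word that leaves the list open. That stands: a reader might infer that the investigators have chosen the standard error specifically for the primary proportion, and the documents do not say so. But the proportion is an outcome variable, adverse events are named outright, and an open list that names no interval still leaves none prespecified.

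A second reply is that no Wald interval is planned. That also stands. A reader might infer that the plan overstates the lower confidence limit, by 17 points at 20/20 (100 − 83.2) and 10 at 19/20 (85.4 − 75.1). There is no planned lower limit to overstate; those gaps arise only if someone forms a symmetric interval from the standard error. Nor is the 19/20 standard error itself faulty: 4.9 points equals the true standard error if the true rate is 95%.

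Third, this is a descriptive pilot with no decision rule, and anyone given the count and denominator can compute an exact interval. That limits the consequence to reporting. It does not remove it, because without a test the estimate and its uncertainty are what the trial delivers on efficacy, and the plan does not commit to reporting the count over its denominator.

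Finally, 20/20 may not occur. The cited 3/282 comes from another population, its complement may include subjects with missing data, and Section 12 allows treatment to be held or stopped. At 16/20, for example, the symmetric interval (62.5–97.5%) no longer passes 100%, although the exact one (56.3–94.3%) still lies lower.

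**Conclusion.** The concern holds as an omission with a specific consequence. Followed as written, the plan attaches a standard error of exactly 0 to a result that it regards as plausible, when the exact 95% interval reaches down to 83.2% (81.5% if N is 18). It does the same for any adverse event or rejection with a zero count, where a true rate up to 16.8% in 20 subjects is not excluded. These limits need only the binomial model and the denominator; they do not depend on an assumed suppression rate. The likelihood of seeing 20/20 does depend on one, and runs from 12% to 82% over assumed true rates of 90% to 99%.

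The documents do not support going further. No error rate, decision or sample size is affected, no faulty interval has been adopted, and the standard error just below the boundary is a legitimate quantity that is merely a poor basis for a symmetric interval. This is a reporting change worth making before analysis, not a flaw in the design.

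**What to change.** Make the same edit in Section 3.1 (Statistical Analyses and Sample Size) and Section 10.1, since changing only one would leave two conflicting statements. Suggested wording: the proportion with HIV-1 RNA below 50 copies/mL at week 48, and all other binary outcomes including adverse events and graft rejection, will be reported as count over denominator with a two-sided 95% Clopper-Pearson confidence interval; means, medians, ranges and standard errors will be used for continuous outcomes only. Wilson is an acceptable alternative, provided one method is named in advance.

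The denominator should be settled at the same time, because Section 3.1 gives both eighteen and 20 as the enrolment figure.

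The cost is a sentence in each of two sections and a line of code, with no new data, visits or subjects. The stated precision will be wider and less favourable: at 20/20 the report would show 83.2% to 100% in place of a standard error of 0.

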2. Safety and tolerability (monitoring and recording adverse events) in subjects who switched from a prior ARV regimen to BIC/F/TAF.
3. Pharmacokinetics of BIC/F/TAF and tacrolimus, including intracellular TAF levels (dried blood spot, PBMC).

Secondary Endpoints:

1. Changes from baseline in CD4+ T lymphocyte cell count/percentages post renal transplant.
2. Incidence of rejection rates of the kidney transplant post renal transplant and correlation with tacrolimus levels.
3. Patient satisfaction with reduced pill burden and adverse events with BIC/F/TAF.

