Kidney transplantation is successful in HIV+ patients although rejection rates are higher than in non-HIV+ transplant patients (8). The greatest clinical challenge is to achieve therapeutic and nontoxic levels of the immunosuppressive drugs, especially Tacrolimus, in this population, due to the complicated pharmacokinetic interactions of these agents with antiretroviral agents (ARV), especially protease inhibitors, cobicistat, and ritonavir (8). Non-therapeutic exposure to tacrolimus contributes to higher rate of rejection, so it is important to study ARV agents with less drug-drug interactions that are safe in this special population. We are currently completing a manuscript addressing this issue at our institution and the kidney transplant team has presented preliminary data in a poster at the American Transplant Congress in 2018 (Al Jurdi, Clinical Outcomes of HIV-Infected Kidney Transplant Recipients With An Early Corticosteroid Withdrawal Protocol). It is important to closely follow the CD4 lymphocyte counts and percentages in this unique population and the effect on HIV infection and immunosuppression. Preferred ARV regimens in HIV+ patients post renal transplant include integrase inhibitors and TAF, with the goal to avoid protease inhibitors, ritonavir and cobicistat and decrease drug-drug interactions with tacrolimus (8,9).

In treatment naïve adults with HIV-1 infection, switching from DTG, abacavir, and lamivudine to BIC/F/TAF proved to be a safe and efficacious option for the treatment of HIV-1 infection (1). The pharmacokinetics of BIC/F/TAF were assessed in this study, and the mean trough concentrations of BIC were 14 times higher than the protein-adjusted 95% effective concentration against wild type HIV-1 virus.

There is no current data about the pharmacokinetics of BIC/F/TAF in renal transplant recipients or the interactions of BIC/F/TAF with tacrolimus. Previous work has demonstrated sustained, zero-order, linear, release pharmacokinetic characteristics of TAF (10,11). TAF is metabolized via CES1 in hepatocytes, cathepsin A in PBMCs, and minimally with CYP3A. Tenofovir plasma levels significantly increase when administered to subjects with moderate to severe renal impairment, such that the dosing interval is adjusted in patients with baseline creatinine clearance below 50 mL/min based on modeling of single-dose pharmacokinetic data in non-HIV and non-HBV infected subjects with varying degrees of renal impairment (12).

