^f Clinical Safety Labs include: CBC, complete metabolic panel, urinalysis, eGFR, urine protein/creatinine ratio, urine albumin/creatinine ratio, phosphorus, retinol binding protein, and beta 2 microglobulin. For subjects enrolled in Group 2, all standard of care lab values and concomitant medications will be collected for 60] days prior to the Biktarvy switch date and the duration of Biktarvy therapy will also be recorded.

^g Three samples will be collected on W12 at 0, 4, and 24 hours (the 24 hour time point is optional, if feasible), and 1 sample will be collected at visits W24, W36, and W48, and FU – M6. Stored samples will be sent to [name] at the University of Colorado's Antiviral Laboratory.

^h Three samples will be collected on W12 at 0, 4, and 24 hours (the 24 hour time point is optional, if feasible). Stored samples will be sent to [name] at the University of Colorado's Antiviral Laboratory.

ⁱ Six samples will be collected on W12 at 0, 0.5, 1, 2, 4, and 24 hours (the 24 hour time point is optional, if feasible). Pharmacokinetic testing for Group 2 subjects will be completed once the subject's tacrolimus levels are stable as per the Principal Investigator for 2-4 weeks.

^j The study visits and bloodwork at these timepoints will be optional, to be completed as needed, as per the investigator.

^k If a subject needs to stop treatment as per the Data and Safety Monitoring Plan (Section 12), the subject will be seen as soon as possible for an Unscheduled Visit and will continue to be followed for the duration of the study as per the Schedule of Assessments for non-terminated patients.

Informed consent will be obtained on Day 1 or up to 2 months prior to Day 1, before starting the study (switch day) (Section 6.1).

Patients will have bloodwork completed throughout the study, as shown in the Schedule of Assessments (Section 6.1).

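### Tacrolimus pharmacokinetics are part of a primary endpoint, but no tacrolimus parameter or pre/post-switch comparison is defined and dose enters no analysis, so stable levels alone cannot show few interactions

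*Combined protocol and SAP*

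**What the plan says.** Among the synopsis primary endpoints is "Pharmacokinetics of BIC/F/TAF and tacrolimus, including intracellular TAF levels (dried blood spot, PBMC". Primary objective 3 covers the pharmacokinetics of BIC/F/TAF and "its interactions with immunosuppressive agents (Tacrolimus) at 12 weeks post-switch to BIC/F/TAF". The hypothesis in Section 3.1 is that interactions with tacrolimus will be few.

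The pharmacokinetic methods in Section 3.1 are written for the study drug: "The pharmacokinetic variables for BIC/F/TAF are calculated from the concentration-time data using noncompartmental methods". The assay described there is also for the study drug: "BIC, F, and TAF in plasma are assayed using a validated LC/MS/MS methodology".

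Tacrolimus is named in these places, each time as a level:
- the regression in Sections 3.1 and 10.1: "The relationship between renal function, tacrolimus levels, BIC/F/TAF plasma concentrations, and intracellular concentrations of TAF will be determined by linear regression analysis";
- primary objective 4 (synopsis and Section 1.2.1), among the renal biomarkers;
- a secondary endpoint: "Incidence of rejection rates of the kidney transplant post renal transplant and correlation with tacrolimus levels";
- the Schedule of Assessments (Section 6.1) and the safety board listing (Section 12).

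The plan also treats the level as something clinicians control. Section 2 says: "The greatest clinical challenge is to achieve therapeutic and nontoxic levels of the immunosuppressive drugs, especially Tacrolimus, in this population". The expected outcomes in Section 10.1 pair stable levels with minimal interactions that are easily adjusted for. Section 12 lists failure to control levels as a possible reason to end protocol treatment. For Group 2 (subjects already switched before they were identified for the study), pharmacokinetic testing waits until levels have been stable for 2-4 weeks.

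**The concern.** An interaction is a change in how the body handles tacrolimus. If the dose is changed to bring the level back to target, the level returns to where it was and the interaction shows in the dose. An analysis of levels without dose can then look near null although clearance has changed.

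The risk is foreseeable here. Section 2 says that 33 of 37 candidate patients are on various regimens, including protease inhibitors, cobicistat and ritonavir, and that these increase interactions with tacrolimus. Stopping a booster at the switch is thus a plausible reason for clearance to change.

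At stake is what the trial may conclude on a primary objective. Stable levels are a valid result about manageability. They do not show that clearance was unchanged.

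**Working it through.** **No figure to reproduce.** The documents give no tacrolimus effect size, variability, no-interaction bound, alpha or power. They give n = 20 (synopsis, Sections 3.1, 4.6 and 10.1) and, at the start of Section 3.1, 18. Everything else below is assumed and shown over a range.

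**Step 1: what dose adjustment does to the level.** Assume linear steady state and the same time since dose at both levels, so that level is proportional to dose/clearance. Let F be the fold change in clearance and a the share of the log change that dosing offsets. Then
- raw post/pre level ratio = F^-(1-a);
- post/pre level/dose ratio = 1/F.

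| F (assumed) | raw, a = 0 | raw, a = 0.5 | raw, a = 0.9 | raw, a = 1 | level/dose, any a |
|---|---|---|---|---|---|
| 1.5 | 0.67 | 0.82 | 0.96 | 1.00 | 0.67 |
| 2 | 0.50 | 0.71 | 0.93 | 1.00 | 0.50 |
| 4 | 0.25 | 0.50 | 0.87 | 1.00 | 0.25 |

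For example, F = 2 and a = 0.9 gives 2^-0.1 = 0.93. At a = 0 the two measures agree and nothing is lost.

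**Step 2: what that does to detection.** The plan specifies no test, so this is illustration only. In simulated paired t-tests on log ratios (two-sided 5%, n = 20, assumed within-subject CV 30%, F = 1.5 in everyone), raw levels detect the change in 98.5%, 54.1% and 4.8% of runs at a = 0, 0.5 and 1. Level/dose detects it in 98.6% throughout. At an assumed CV of 50% the raw figures are about 73%, 25% and 5%, against 73% for level/dose.

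**Step 3: why a level/dose ratio must be split by prior regimen.** Suppose k of 20 subjects were boosted (the number is not given), clearance rises F-fold in them from booster removal alone, and BIC/F/TAF has no effect. The pooled ratio is F^(-k/20):

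| F | k = 5 | k = 10 | k = 15 |
|---|---|---|---|
| 1.5 | 0.90 | 0.82 | 0.74 |
| 2 | 0.84 | 0.71 | 0.59 |
| 4 | 0.71 | 0.50 | 0.35 |

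All of these would look like an effect of the study drug.

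**Step 4: precision of the ratio.** With one level before and one after the switch, the 90% CI limits are the ratio multiplied and divided by exp(t(0.95, n-1) × sqrt((2s² + τ²)/n)), where s² = ln(1 + CV²) and τ is the between-subject SD of the log fold change. At CV 30%, s² = ln(1.09) = 0.0862.
- n = 20, τ = 0: exp(1.729 × sqrt(0.1724/20)) = 1.17. With τ = 0.3, 0.5 and 0.7 it is 1.22, 1.29 and 1.37. Over CV 20-40% and τ 0-0.7 the range is 1.11-1.41.
- n = 18: 1.19-1.40 over τ 0-0.7 at CV 30%.
- n = 10: 1.27-1.60.
- n = 5: 1.49-2.17.

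A simulation of 20,000 trials per τ (F = 2, n = 20, CV 30%) gave coverage of 89.8-90.0%. The plan's own variability figure, a coefficient of variation below 15% for the pharmacokinetic studies, is not tied to tacrolimus.

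**The case against.** The best defence is that this is a descriptive pilot sized by feasibility, and that expecting few, easily adjusted interactions is largely a claim of manageability, which levels do address. That stands in part: no test or power is asked for. A descriptive primary endpoint still needs a defined variable, and none is defined for tacrolimus.

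Four stronger readings are tempting, and the documents do not support them.
- *Only raw levels will be analysed.* The sentence on descriptive statistics names no tacrolimus measure. What can be said is that the measure is undefined and that every named one is a level.
- *The intensive sampling excludes tacrolimus.* The footnote says "Six samples will be collected on W12 at 0, 0.5, 1, 2, 4, and 24 hours" and lists no analyte at all, not even the study drug's components. Its silence proves nothing.
- *The sponsor will infer unchanged clearance from stable levels.* No passage says so. Section 10.1 also does not name what is adjusted; tacrolimus dose is the natural reading, given the Section 12 wording on control of levels.
- *Dose will not be recorded.* Section 8 has all treatment data captured in REDCap, and Group 2 concomitant medications are collected. Dose may well be in the charts. It is not named, linked to a level or analysed.

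Levels scheduled at Weeks 4 and 8, optional levels on Days 3-22 and reports of uncontrolled levels could reveal a large or fast change. They help less for Group 2, whose Day 1 falls after the switch. The gain from the remedy is also limited: in previously boosted subjects it cannot separate booster removal from BIC/F/TAF, and the size of the unboosted group is unknown.

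**Conclusion.** The concern holds as a gap in definition with a conditional consequence. A named primary endpoint has no tacrolimus parameter and no pre/post-switch comparison, and tacrolimus dose is in no analysis. Raw levels understate a clearance change to the extent that dosing offsets it. The size in this trial cannot be stated, because the documents do not say how far or how fast doses are adjusted. For an assumed doubling of clearance the raw ratio lies anywhere from 0.50 to 1.00 against a constant 0.50 for level/dose. This rests on linear steady state and comparable sampling times. The change should be made before analysis; it does not call the trial's conduct into question.

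**What to change.** Define the tacrolimus endpoint as the within-subject ratio of level/dose about 12 weeks after the actual switch date to level/dose before the switch. Report it as a geometric mean ratio with 90% CI, beside the raw levels and the change in dose, separately for prior boosted and unboosted regimens. Do not read a pooled ratio as the effect of BIC/F/TAF.

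For the levels used, take from the chart the total daily tacrolimus dose, the formulation, the date of the last dose change and, where available, the time since the last dose. Add prior regimen for each subject and the switch date for Group 2. The pre-switch value is Day 1 or, for Group 2, the standard-of-care record from the 60 days before the switch. State before analysis what counts as a stable dose and a comparable sampling time.

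Reconcile two passages on Group 2. Section 3.1 has standard-of-care labs and concomitant medications collected for 60 days before and after the switch and for as long as therapy lasts. Footnote f in Section 6.1 gives the 60 days before the switch and can be read as recording only the length of therapy after it. The Group 2 post-switch value depends on the answer.

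Cost: four fields × two levels × 20 subjects = 160 entries, plus prior regimen and switch date; no new samples or visits. Group 2 records and sampling times may be incomplete, and excluding non-comparable levels reduces the usable number. Intervals are wide after the split, as the n = 10 and n = 5 factors show. No change to clinical management is proposed.
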